**Vapotherm, Inc**  
**Hypercapnia Stabilization RCT NIPPV v HVNI**  
**Confidential**

## II. Overall Study Objective

The **overall objective** of this randomized study is to evaluate the efficacy of HVNI, in comparison to NIPPV, to clinically stabilize and provide respiratory therapy to patients who have COPD with moderate-to-severe hypercapnic respiratory distress upon presentation.

The **hypothesis**: HVNI is comparable to NIPPV in the stabilization and relief of moderate-to-severe hypercapnic respiratory distress upon presentation, by relieving the patient's dyspnea (breathlessness) within 4 hours to a comparable degree to NIPPV.

$$H_0: \mu_T \leq \mu_C - 1$$

$$H_a: \mu_T > \mu_C - 1,$$

where  $\mu_T$  and  $\mu_C$  are the improvement in modified BORG at 4 hours for treatment (Vapotherm) and control (NIPPV), respectively, and the non-inferiority margin is 1.

To test this hypothesis, the study will be conducted with the following specific aims:

**Aim #1: Primary Outcome.** The primary endpoint is to evaluate the patient's relief of dyspnea, as measured by the modified Borg, rated perceived dyspnea [RPD 0-10], during the 4-hour post-therapy initiation interval. These measurements will be compiled over the time course of the study – baseline, 30min, 1h, and 4h.

**Aim #2: Secondary Outcomes.** The secondary endpoints evaluate treatment failure (need for intubation), indices of Work of Breathing (patient vitals [HR, RR, SpO2]), patient's clinical stability during hypercapnic respiratory distress, as measured by an index of patient communication capability [Patient Stability Index: 0-10], venous blood gases (pH, PCO2, PO2, bicarbonate, base excess), basic metabolic panel\* (lactate, Na+, K+, Cl, glucose), and patient disposition (length of stay [LOS]). These measurements will be compiled over the time course of the study – baseline\*, 30min, 1h, and 4h. The Patient Stability Index is described in the protocol.

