**Vapotherm, Inc**  
**Hypercapnia Stabilization RCT NIPPV v HVNI**  
**Confidential**

#### **IV. Study Design**

This will be performed as a prospective, unblinded (by definition), multicenter, 1:1 randomized non-inferiority design clinical trial to evaluate the efficacy of HVNI compared to NIPPV (two approved interventions for the management of acute respiratory distress) in the clinical stabilization and relief of moderate-to-severe respiratory distress requiring ventilatory support upon presentation. Patients deemed to fit the criteria for inclusion will perform the study procedures for one of the study arms of the randomized study design. Patient completion of either of the study arms will provide an evaluation of the efficacy of HVNI or NIPPV in stabilization and relief of respiratory acidosis and will record patient ventilatory/WOB indices, treatment failure, disposition, and physiologic parameters during a 4-hour therapy-response window. Additionally, tertiary outcomes will provide an evaluation of patient comfort, and therapeutic response, per the study aims. Patients are expected to complete the study in one session, per the noted parameter sampling intervals (baseline, 30min, 1hr, 4hr). After the patient completes the randomized study arm (HVNI or NIPPV), the clinicians and patients will complete perception score assessments. The clinical management will otherwise remain unchanged, based on individual study site standard of care and practice.

This study will utilize two arms. Patients presenting with acute hypercapnic respiratory failure (per Inclusion criteria, in need of clinical stabilization and relief of moderate-to-severe respiratory distress) who are escalated to treatment with a non-invasive respiratory support modality will be randomized to one of the following:

- Vapotherm high flow nasal cannula therapy (HVNI) administered as defined below (HVNI arm)
- Non-invasive positive pressure ventilation (NIPPV) delivered via single-limb circuit with a full face mask using a pressure support mechanical ventilator system (e.g., Resironics Vision, V60) administered as defined below (NIPPV arm)

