The study design will focus on six distinct phases for each study arm, which will be identical except for the therapy randomization (HVNI or NIPPV): (1) Study Start, (2) Baseline Characterization, (3) Therapy Evaluation Interval 1, (4) Therapy Evaluation Interval 2, (5) Therapy Evaluation Interval 3, and (6) Study End. Primary, secondary, and tertiary outcomes will be completed upon the completion of all study phases.

The Study Start Phase will follow screening and consent, and will confirm randomization to either study arm, and gather the patient background, history, health, demographics, and current respiratory therapies. For Phase 2, Baseline Characterization will provide the initial clinical evaluation along with the baseline physiologic parameters, ventilation parameters, Patient Stability Index, and blood gases. For Phase 3, the Therapy Interval 1 will provide the current patient status at 30minutes post randomized therapy interval and will include this interval's physiologic parameters, ventilation parameters, Patient Stability Index, and venous blood gases. For Phase 4, the Therapy Interval 2 will provide the current patient status at 1hour post randomized therapy interval and will include this interval's physiologic parameters, ventilation parameters, Patient Stability Index, and venous blood gases. For Phase 5, the Therapy Interval 3 will provide the current patient status at 4-hour post randomized therapy interval and will include this interval's physiologic parameters, ventilation parameters, Patient Stability Index, and venous blood gases. Following the 3rd Therapy Evaluation Interval at 4hours, Phase 6 will be implemented, which concludes with Study End. Phase 6 will include Visual Analog Scale (VAS) for both patient and clinician assessment scores. The clinician and the patient will complete VAS perception scores for their randomized study arm (HVNI or NIPPV) at designated intervals.

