**Phase 2 – Baseline Characterization**

The baseline characterization will provide the initial clinical evaluation. Upon enrollment, randomization, and patient background collection, an venous blood gas sample will be drawn to establish the patient baseline at the time just prior to placing the patient on either of the study arm therapies (HVNI or NIPPV). Patient baseline for physiologic parameters (RR, HR, SpO2, BP, RPD) and venous blood gas parameters (PCO2, PO2, pH, bicarbonate, base excess,) will be collected at this time, prior to the initiation of the assigned/randomized therapy. A basic metabolic panel (BUN, CO2, Creatinine, Glucose, Chloride, Potassium, Sodium, Calcium) will also be collected at this time. For the RPD, the clinician will record patient scores. Patient Stability Index evaluation will be evaluated by clinicians and recorded at this time, described as follows: to assess patient clinical stability using a continuous VAS score on a scale from unable to speak, due to severe respiratory distress, up to speaks in full sentences without severe respiratory distress.

At baseline, only patient perception scores will take place. During the noted study phases, the clinician and the patient will complete VAS perception scores (annotated on 100mm line with an "X") for their randomized study arm (HVNI or NIPPV). Patient & Clinician Perception Assessment will be performed by the clinician or therapist performing or participating in the testing procedures. The Perception Assessments will be completed for each of the three endpoints for clinician assessment and the two endpoints for the patient assessment. For the patient perception/satisfaction these include: (1) relief of symptoms, and (2) comfort/tolerance. For the clinician perceptions these include: (1) expected/perceived patient outcomes, (2) patient comfort & tolerance, and (3) ease of use.

The assigned therapy per randomization will be implemented per the initial settings identified below, after which settings will be titrated per standard practice for optimal effect. Patients will be managed by routine care while study data is captured as per the timeline given in Table 1. Note: All decision making for intubation, treatment regimen, discharge, and disposition will be made per standard practice at each center using the judgment of the PI, Sub-I or their designee.

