### Primary Endpoint

- Primary Parameter – Change in modified Borg (RPD) over 4-hours

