## VIII. Statistical Analysis

The data analysis will be “per protocol,” and per the “intention-to-treat” model. Baseline patient demographics and characteristics will be summarized, compared, and appropriate statistical testing will be performed for the continuous and categorical variables. Primary outcomes will be analyzed for statistical significance to test the null hypothesis. Assuming a non-normal data distribution for this randomized study design, the non-parametric Wilcoxon Signed Rank Sum test will be performed with significance interval of 0.05 on all applicable variables. Parametric analytical analogues (e.g. t-test) will be used if the measurements present a normal distribution. Otherwise, for the categorical variables, the Fisher’s Exact test will be performed and shown by category. Data for patient parameters will be compared across treatment arms and time-period using Repeated Measures analysis ANOVAs to assess dependence on treatment and interactions with time. Data will be compared and graphed accordingly for a visual comparison with accompanied statistical notations. Significance will be accepted where  $p < 0.05$ . Analyses will be performed using SAS version 9.2 or higher or comparable statistical software.

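### The repeated-measures ANOVA in Section VIII does not fix the role of baseline or name the contrast that estimates the 4-hour difference; if baseline is an outcome level, the treatment main effect is 75% of the post-baseline average

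*Combined protocol and SAP*

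**What the plan says.** Section VIII (Statistical Analysis) plans that patient data "will be compared across treatment arms and time-period using Repeated Measures analysis ANOVAs to assess dependence on treatment and interactions with time". It gives no levels for time, no covariate and no contrast. Significance is set at p < 0.05.

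The times have to be taken from other sections. Section II gives them, for both the primary and the secondary outcomes, as "baseline, 30min, 1h, and 4h", and Section IV repeats the same four. Section IV also names baseline characterisation as a phase of its own, apart from three therapy evaluation intervals. Under Phase 2 in Section VI, baseline readings are taken "prior to the initiation of the assigned/randomized therapy". Among the secondary endpoints in Section VII, only the blood gases are worded as changes; SpO2, HR, RR, BP and the Patient Stability Index are not.

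For the primary outcome, Section VII names "Change in modified Borg (RPD) over 4-hours". The two means in the Section II hypothesis "are the improvement in modified BORG at 4 hours for treatment (Vapotherm) and control (NIPPV), respectively". For testing, Section VIII says that "the non-parametric Wilcoxon Signed Rank Sum test will be performed with significance interval of 0.05 on all applicable variables", with a t-test if the data are normal.

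**The concern.** A repeated-measures ANOVA reports a treatment main effect, a time effect and their interaction. Section VIII speaks of dependence on treatment, which most naturally points to the main effect. If baseline is one of the time levels, that main effect averages in a reading that therapy cannot have influenced.

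The direction matters. Section II says that the endpoints will establish comparability of the two therapies, and Section VIII judges results by p < 0.05, with no margin for the secondary endpoints. An estimate pulled toward zero makes a finding of no difference more likely. For HR, RR, SpO2, BP, blood gases and the Stability Index, this ANOVA is the only longitudinal analysis the plan describes.

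**Working it through.** **The plan's own figure.** The sample size rests on the 4-hour Borg change, not on the ANOVA. Section V gives a difference of 0.9 in favour of HVNI, SDs of 2.4 and 2.9, a margin of 1.0, one-sided alpha of 0.025 and 32 per arm.

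- SE = sqrt((2.4² + 2.9²)/32) = sqrt(14.17/32) = 0.665.
- Distance from the margin = 0.9 + 1.0 = 1.9, and 1.9/0.665 = 2.86.
- Power from the noncentral t is 80.3%, so the stated 64 is reproduced.

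**Main effect with baseline as a level.** With complete, balanced data the treatment main effect is the plain mean of the arm differences over the time levels. Write d30, d60 and d240 for the differences at 30 min, 1 h and 4 h. The expected baseline difference is 0 by randomisation.

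- Four levels: (0 + d30 + d60 + d240)/4.
- Three post-baseline levels: (d30 + d60 + d240)/3.
- Ratio: 3/4, whatever the profile.

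The share of the 4-hour difference recovered does depend on the profile. The documents give no arm differences at 30 min or 1 h, so every profile below is an assumption.

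| Assumed d30, d60, d240 as share of d240 | Four levels | Three levels |
|---|---|---|
| 1, 1, 1 | 0.750 | 1.000 |
| 1/2, 3/4, 1 | 0.562 | 0.750 |
| 1/3, 1/2, 1 | 0.458 | 0.611 |
| 1/8, 1/4, 1 (linear in hours) | 0.344 | 0.458 |
| 0, 0, 1 | 0.250 | 0.333 |
| 4/3, 4/3, 1 (early peak) | 0.917 | 1.222 |

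The shortfall against the 4-hour difference therefore runs from 8% to 75% over these profiles. Baseline contributes only the fixed factor of 3/4. The rest is the averaging of 30 min and 1 h, which remains when baseline is dropped.

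**Interaction.** With baseline kept as a level, the contrast (4 h minus baseline, HVNI) minus (4 h minus baseline, NIPPV) has expectation d240 − 0 = d240. In a simulation with 32 per arm, a true 4-hour difference of 0.9, an assumed correlation of 0.5 and a change SD of 2.66, it averaged 0.89 to 0.90 over four profiles. That contrast is the difference in raw change.

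**Gain from adjusting for baseline.** Assume equal variance s² at baseline and 4 h, and correlation r. The per-patient variance of the raw change is 2s²(1 − r). The variance of the 4-hour value adjusted for baseline is s²(1 − r²). The ratio is (1 + r)/2.

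- r = 0.3: 0.65, a 35% reduction.
- r = 0.5: 0.75, a 25% reduction.
- r = 0.7: 0.85, a 15% reduction.

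**The case against.** The strongest reply is that the documents never say that baseline is a level of the ANOVA. Section IV sets it apart from the three therapy intervals. Section VII words the blood gas endpoints as changes, and a change score would make a baseline level zero for every patient. A three-level or change-score model fits the text too. This stands, so the dilution can only be stated conditionally.

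The second reply is that the same sentence in Section VIII also covers interactions with time, which carry the undiluted 4-hour difference. This stands in part. The information is in the model, but the plan names no 4-hour contrast, and an omnibus interaction test gives neither an estimate nor an interval.

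Two stronger readings are tempting and are not supported.

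- A reader might infer a definite bias in the 4-hour difference, such as 25% to 54%. Those figures belong to particular assumed profiles (the first and third rows of the table), and part of the larger one is not due to baseline.
- A reader might set the main effect against the 1-point Borg margin, so that a constant deficit of 1.33 reads as 0.75 × 1.33 = 1.0. Nothing in the plan makes that comparison. The hypothesis concerns improvement at 4 hours, Section VIII names a Wilcoxon or t-test alongside the test of the null, and the secondary parameters have no margin.

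**Conclusion.** The point holds as a gap in specification. Section VIII leaves open whether baseline is an outcome level or a covariate, and which contrast estimates the 4-hour difference. If the main effect over the four listed times is interpreted, it is 75% of the post-baseline average. That factor needs only randomisation, complete balanced data and equal weighting of the four times. No single figure can be given for the shortfall against the 4-hour difference.

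The consequence falls mainly on HR, RR, SpO2, BP, blood gases and the Stability Index, and on any supportive Borg analysis. It does not show that the primary non-inferiority test is biased. The change is worth making under any reading of the time levels, because it names the 4-hour estimate and uses a baseline that the trial already collects. The variance reduction of 15% to 35% is relative to the raw change and is an illustration that rests on the assumed correlations and equal variances.

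**What to change.** In Section VIII, replace the repeated-measures sentence with a full specification:

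- Outcomes are the values at 30 min, 1 h and 4 h.
- The patient's own baseline value is a covariate, with treatment, time and treatment-by-time as the other terms.
- The reported result for each parameter is the arm contrast at 4 h with its 95% CI.
- A main effect averaged over baseline is not interpreted.

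The cost is a short change of text. The visits, data and software stay the same. If a three-level model was already intended, the new text makes that explicit and adds the baseline adjustment and the 4-hour contrast.

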### **Sample Size:**

This trial will randomize subjects 1:1 to Vapotherm:NIPPV. A total sample size of 64 subjects (~32 per arm) randomized with endpoint data, and a one-sided alpha of 0.025 will provide at least 80% power to demonstrate non-inferiority. This sample size assumes a difference of 0.9 between treatment and control with standard deviation of 2.4 and 2.9 for treatment and control, respectively, and a non-inferiority margin of 1.0.

Allowing for up to 20% attrition, approximately 80 subjects (40 per arm) will be enrolled in order to achieve 64 subjects with an endpoint.

From Doshi et al, comparable moderate-to-severe hypercapnic respiratory distress patient data was analyzed, which informed this sample size calculation's assumed difference and standard deviations in treatment (HVNI) and control (NIPPV) for the modified Borg score.

Change in modified Borg over 4 hours	Mean	Standard Deviation
NIPPV arm (Control)	-3.208	2.431
HVNI arm (Treatment)	-4.143	2.931

The minimal clinically important difference (MCID) for modified Borg was informed from literature, as a difference value of 1.0.

**NOTE:** As this is an Emergency Department or inpatient acute care study, and treatment is often immediate due to need for maintaining patient safety, there is an expected patient dropout (i.e. incomplete or unusable subject number) of randomized & enrolled patients into this study. After presenting to the ED or inpatient acute care setting, should the patients be transferred to another area of the hospital, the study procedures will continue until complete.

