#### Screening, Enrollment, & Management

Upon screening and fitting subject selection criteria, known at time of presentation to the ED or Acute Care unit for treatment, subjects may or may not be able to be asked to be randomized and enrolled into this study. In ED or Acute Care settings, there is a need to treat immediately to maintain patient safety. As such, consent in this study will take place through verbal consent prior to participation/randomization followed by written consent (when respiratory symptoms are manageable), or written consent prior to participation/randomization. Patients will be reassured that their medical care will not be impacted in any way and their medical providers will not change. All patients randomized, but not included in the final study population, will be accounted for in a CONSORT diagram, noting the dropout criteria (i.e. refused consent, met exclusion criteria, incomplete dataset, etc.). All study procedures will be explained to the subject.

Subjects will be managed by routine care while study data is captured as shown in the timeline below (Table 1). All decision making for patient participation will be made per standard practice/care at the trial site, relying on the judgment of qualified medical professionals on staff.

**Figure 1. Framework of the clinical study procedures discussed within this protocol for the two study arms: HVNI and NIPPV.**

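### The planned repeated-measures ANOVA can drop patients who have usable readings; a mixed model would keep them, and the plan should name the analysis that decides the primary hypothesis

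*Combined protocol and SAP*

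**What the plan says.** Section II schedules readings at "baseline, 30min, 1h, and 4h". Section VIII (Statistical Analysis) gives one longitudinal method for the patient measurements: "Repeated Measures analysis ANOVAs to assess dependence on treatment and interactions with time". It names no covariance structure, SAS procedure or missing-data rule; on software it says only "Analyses will be performed using SAS version 9.2 or higher or comparable statistical software". A separate sentence covers simple comparisons: "the non-parametric Wilcoxon Signed Rank Sum test will be performed with significance interval of 0.05 on all applicable variables", with a t-test where the data look normal. The analysis sets are given as: "The data analysis will be “per protocol,” and per the “intention-to-treat” model".

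Incomplete data are anticipated. The sample size note says "there is an expected patient dropout (i.e. incomplete or unusable subject number) of randomized & enrolled patients into this study", and about 80 patients are to be enrolled so that 64 have an endpoint. Under Screening, Enrollment, & Management, "incomplete dataset" is one of the listed reasons why a randomized patient may not be in the final study population.

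The primary endpoint is the Borg change to 4 hours (Sections II and VII). Section II also says that Borg is compiled at all four times.

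**The concern.** Classical repeated-measures ANOVA works on a complete patient-by-time table. A patient with valid baseline, 1-hour and 4-hour values but no 30-minute value leaves the analysis altogether. The univariate time tests also assume sphericity. The gaps between readings are 30 minutes, 30 minutes and 3 hours, so equal variances of all pairwise differences are hard to take for granted.

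Gaps are plausible here. Patients may be moved between units, and Section VII sets a window of plus or minus 5 (no unit printed) for vital signs and indices. After early intubation or ED discharge the reading is taken at that moment, and the plan does not say which time point it then represents.

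At stake is whether the time-course results, mainly for the secondary endpoints, describe all randomized patients with data or only those with a full set. If the same model were applied to Borg, the primary sample would be exposed too.

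**Working it through.** **Inputs from the Sample Size section:** 32 per arm with an endpoint (64 in all), 40 per arm enrolled, SDs 2.4 and 2.9, assumed difference 0.9 in favour of HVNI, margin 1.0, one-sided alpha 0.025. The section's table attaches the two SDs to the opposite arms; with 1:1 allocation this leaves the results unchanged.

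**Step 1, the plan's own figures.** At 32 per arm the standard error is sqrt(2.4²/32 + 2.9²/32) = 0.665. The distance from the margin is 0.9 + 1.0 = 1.9, so the noncentrality is 1.9/0.665 = 2.855. With Welch degrees of freedom of about 59.9, noncentral-t power is 80.2%. Enrolment is 64/0.8 = 80. Both of the plan's numbers reproduce.

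**Step 2, complete cases if the model is used for Borg.** The documents give no missingness rates. Assume that a fraction q of patients misses each of the 30-minute and 1-hour readings independently. Complete cases per arm are then n × (1 − q)². The starting n matters:

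| q (assumed) | From 32 (gaps on top of a fully used 20%) | Power | From 40 (gaps are the only loss) | Power |
|---|---|---|---|---|
| 5% | 28.9 | 75.9% | 36.1 | 84.8% |
| 10% | 25.9 | 71.2% | 32.4 | 80.7% |
| 15% | 23.1 | 66.0% | 28.9 | 76.0% |

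Independence is the harsher assumption. If the same 10% of patients missed both middle readings, 32 × 0.90 = 28.8 per arm would remain, not 25.9.

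**Step 3, methods side by side.** This uses a normal approximation with pooled SD sqrt((2.4² + 2.9²)/2) = 2.662, compound symmetry, an assumed within-patient correlation of 0.3 to 0.7 and data missing at random. The mixed model here treats baseline as one of the four outcomes. Each case starts from 40 per arm.

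| Pattern of loss per arm (assumed) | Repeated-measures ANOVA | 4-hour change test | Mixed model |
|---|---|---|---|
| 8 have nothing after baseline | n = 32, 81.5% | n = 32, 81.5% | effective n 33.0–34.4, 82.6–84.2% |
| 8 miss only the 4-hour reading | n = 32, 81.5% | n = 32, 81.5% | effective n 34.4–34.8, 84.2–84.6% |
| 8 have nothing after baseline and 6 more miss one middle reading | n = 26, 73.0% | n = 32, 81.5% | effective n 33.0–34.4, 82.6–84.2% |
| 8 miss only one middle reading | n = 32, 81.5% | n = 40, 89.1% | n = 40, 89.1% |

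The loss specific to repeated-measures ANOVA comes from patients who have a 4-hour value but lack a middle one. Where whole patients or the 4-hour value are lost, a mixed model recovers only about 1 to 3 effective patients per arm. A model with baseline as a covariate draws nothing from patients without follow-up, so the small gains in the first and third rows should not be expected from it.

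**The case against.** The strongest reply is that the primary analysis is not affected. The hypothesis and endpoint concern the 4-hour change; Section VIII gives Wilcoxon or a t-test for all applicable variables and puts repeated-measures ANOVA in a different sentence. A change-score test keeps the patient who lacks only a 30-minute reading. This stands. A reader might infer that the method necessarily takes the primary analysis below 64 patients, but the documents do not support that. What remains is that Section VIII assigns no single test to the primary hypothesis.

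Second, the planned 20% already includes incomplete patients, so subtracting them again from 32 may count them twice. This also stands. The fall to 71.2% needs middle-reading gaps on top of a fully used allowance.

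Third, no deletion rule is written, and a likelihood-based repeated-measures fit in SAS would keep partial data. That is correct. Complete-case analysis is the classical reading, and the listing of incomplete datasets as a dropout reason leans towards it, but it is not stated.

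Fourth, a reader might infer that the sickest patients are removed and the arms thereby made to look alike. The documents do not establish that direction. Readings, including dyspnea, are to be taken at intubation or early ED discharge, and procedures continue after transfer. Who would have gaps, and in which arm, is unknown.

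**Conclusion.** The point holds as a weakness in the choice of longitudinal method. The only one named is, in its classical form, the one that wastes partial data, in a trial that expects partial data and promises an intention-to-treat analysis. The exposure is certain in kind for the time-course analyses of vital signs, blood gases, Patient Stability Index and Borg. Its size is unknown, because the documents give neither missingness rates nor within-patient correlations.

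For the primary hypothesis the loss is conditional. It is 4 to 14 percentage points of power (80.2% to between 75.9% and 66.0%) if the model is used for Borg and 5% to 15% of patients miss each middle reading beyond the allowance. It is nil at 10% if those gaps fall within the allowance.

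**What to change.** Replace repeated-measures ANOVA in Section VIII with a mixed model for repeated measures: all post-baseline readings as outcomes, with baseline value, arm, time and arm-by-time as fixed effects and an unstructured covariance. Say how a missing baseline value is handled.

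State that the primary non-inferiority conclusion comes from the 4-hour Borg contrast between arms. Its two-sided 95% confidence interval is set against the margin of 1, so that for improvement on HVNI minus NIPPV the lower limit must lie above −1.

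The model removes selection bias only if data are missing at random, which intubation and early discharge may violate. The plan should therefore state how readings taken at those moments enter the analysis, and should add a sensitivity analysis for data not missing at random.

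The cost is wording in the analysis section and a standard procedure in the named software. No new data and no change to enrolment are needed.
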